4.2 Device Installation

Parents will install the DriveID device via instructions provided with the device. DriveID devices will be installed in all cars driven by the teen-parent dyad. The DriveID device is installed behind the rearview mirror as to not impede vision of the road; the size of the device is approximately 3 inches by 5 inches. The parent and teen will also complete online registration of the device. When installation is completed correctly, a confirmation message is sent to Cellcontrol. If Cellcontrol receives an error message, noting incorrect installation, a member of the study team will contact participants to troubleshoot.

4.3 Study Treatment Phase

The study treatment phase will consist of a baseline measurement period, an intervention and a debriefing period.

4.3.1 Intervention

DriveID will measure participants' trip characteristics (duration, mileage, speed) and cellphone use while the cellphone is in the car in which the DriveID device is installed. DriveID will also record GPS data. This data will not be accessed in real time by the study team and will only be viewed after the completion of the drive.

Coded data on primary and secondary endpoints will be automatically uploaded daily whenever the phone has a Wi-Fi or cellular data connection to the Cellcontrol server and then exported through an encrypted, secure internet connection to Penn's Way to Health IT Platform for management and analysis via linkage of a study ID (as has been established under IRB 14-11234).

After baseline period, parents can view teen trip summaries.

4.3.2 Debriefing

At the completion of Week 8 or upon voluntary withdrawal from the trial, the participants will be instructed to complete an online survey administered through Penn's Way to Health IT platform asking about user satisfaction with the device. They will receive a link to the survey through email. If necessary, they may receive reminder calls from members of the study team for a one month period following study completion. The purpose of the survey will be to debrief the participant's experience with the trial, cellphone blocking technology, and suggestions for designing a better trial. For subjects that withdrawal prematurely, we will ask about what factors contributed to their decision to withdraw early.

For participants who complete the trial, a member of the study team may contact them to complete a brief, semi-structured exit phone interview.

4.4 Subject Completion/Withdrawal

Participants may withdraw from the study at any time. They may also be discontinued from the study at the discretion of the Investigators at any time.

5 STUDY EVALUATIONS AND MEASUREMENTS

5.1 Confirmation of Eligibility

Members of the research team will confirm the eligibility of potential subjects based on the inclusion/exclusion criteria noted in Section 3.4 during the in-person meeting or phone call, after the online consent/assent process. A parent or guardian will first need to create an account on the Way to Health platform and complete consent online. Once consent is obtained, teens will need to create an account on the Way to Health platform and complete assent. After consent and assent are completed, parents and teens will each be presented with a survey to confirm eligibility. If they are eligible, an intake survey will be available for teens to complete. A study team member will contact participants to confirm eligibility. Confirmation of eligibility will be recorded and retained for all individuals. If subjects are not eligible, no other study procedures will occur.

5.2 Intake Survey

We will collect the following information on the parent participant:

- Demographic characteristics
- Driving habits over the previous 30 days
- Attitudes toward in-vehicle cellphone blocking technologies
- Opinions and perceptions on texting while driving and associated technology
- Preferences and use of wireless technology while driving a vehicle

We will collect the following information on the teen participant:

- Driving habits over the previous 30 days
- Use of in-vehicle cell phone blocking technology
- Opinions and perceptions on texting while driving and associated technology
- Month and Year of Birth

5.3 Cellcontrol Data

Cellcontrol requires users to enter in basic information to set up the account policy. This includes:

- Username
- Password
- Name
- Phone number
- Email

The Cellcontrol app currently tabulates the following data which are uploaded securely to the Cellcontrol server:

- Phone talk time while driving
- Phone usage time while driving (non-talk time phone unlocked and being used for apps, texts, email, etc.)
- Phone unlocks while driving
- Speed the car is traveling when the phone is unlocked
- Incidence of hard decelerations converted to a “driving score” and hard accelerations converted to an “eco score”
- Number of incoming calls and texts that are blocked
- GPS, accelerometer, and timestamp data

5.4 End of Baseline Period Survey

We will collect self-report information on each subject’s (both teens and parents) driving behaviors for the previous three weeks in which they were enrolled in the trial study. Information includes how often they report texting and driving and self-report cellphone use.

5.5 End of Study Survey

We will survey participants via the Way To Health platform. The survey will be constructed in Qualtrics, an online survey tool used by Way To Health, to elicit feedback on the cellphone blocking technology. Participants will be asked to report:

- Their feedback on using the cellphone blocking technology
- Feedback on settings/configurations of the cellphone blocking technology
- Perceptions of whether their safety had improved with the use of the technology
- Suggestions for improving the technology and the research study
- Suggestions for future interventions to promote engaged driving

5.6 End of Study Semi-Structured Interview

Approximately 20 teen and 20 parents will be interviewed after completion of the study. Members of the study team will schedule a time to call participants to conduct a brief, semi-structured interview to provide formative data around current strategies to reduce high-risk cellphone use while driving and key elements of an educational, mobile device, and behavioral incentive intervention. The interview will be conducted by a member of the study team and will be recorded by the Penn Mixed Methods Research Lab.

5.7 Safety Evaluation

This is a minimal risk, behavioral intervention study. Physical risk is no more than the risks already caused by distracted driving from handheld cellphone use. The intervention directly lowers the risk of distracted driving by blocking incoming phone calls and texts and locking the phone while the participant is driving. The participant may unlock the phone in any of

the conditions with the tap of a finger where they will then be brought to their typical home screen. If participants have their phone password protected, they will still need to enter their password in order to use the phone. The extra swipe to dismiss the cellphone blocking technology is no more dangerous than unlocking the phone normally.

Participants will have no interaction with the physical DriveID device after installation. There are no expected serious adverse events related to the intervention or participation in this study.

6 STATISTICAL CONSIDERATIONS

This is a pilot trial with the purpose of demonstrating the feasibility of conducting this type of research and generating data in order to estimate sample sizes for future trials.

6.1 Primary Endpoint

In determining feasibility the following endpoints will be measured:

- Proportion of screen eligible who enroll
- Number enrolled per month
- Retention rates by study arm
- Proportion of surveys completed
- Acceptance of cellphone blocking strategy measured on Likert scale in post-study survey

6.2 Secondary Endpoints

Frequency of phone unlocks at non-zero speeds

Total proportion of trip time the phone is in use at non-zero speeds

Total proportion of trip time on non-call related phone use at non-zero speeds

Total proportion of trip time on call-related phone use at non-zero speeds

Total proportion of trip time on non-call related phone use while stopped.

Total proportion of trip time on call-related phone use while stopped.

Seconds of phone use at non-zero speeds

Seconds of phone use while stopped

Number of incoming calls and texts that were blocked

Number of times participants make or receive a phone call, send or read a text message, and use any application while driving at non-zero speeds

Participant acceptance of cellphone blocking technology based on post-study survey

Incidence of handheld cellphone use and its relationship to incoming text messages and driving conditions

6.3 Statistical Methods

6.3.1 Baseline Data

Baseline and demographic characteristics will be summarized by standard descriptive summaries (e.g. means and standard deviations for continuous variables such as age and percentages for categorical variables such as gender).

6.3.2 Efficacy Analysis

The primary analysis will be based on an intention to treat approach and will include all subjects randomized at the beginning of the intervention period.

Primary endpoints on feasibility and acceptability will be tabulated across randomization arms using descriptive statistics.

Secondary efficacy endpoints will be summarized with descriptive statistics across arms and will include:

Frequency of phone unlocks at non-zero speeds

Total proportion of trip time the phone is in use at non-zero speeds

Total proportion of trip time on non-call related phone use at non-zero speeds

Total proportion of trip time on call-related phone use at non-zero speeds

Total proportion of trip time on non-call related phone use while stopped.

Total proportion of trip time on call-related phone use while stopped.

The statistical model used for the efficacy analysis will be tailored to the selected endpoint, but will likely be evaluated with a multilevel model to examine within-subject and across-subject changes over time.

A secondary epidemiologic analysis will examine the driving and environmental characteristics associated with the instant a phone is unlocked at non-zero speeds. This will include vehicle speed, acceleration, time of day, and road and weather characteristics based on GPS location of the phone unlock.

STUDY INTERVENTION

6.4 Description

The study intervention will involve two different conditions to which participants may be randomized.

6.4.1 Teen-Parent Monitoring Group

The blocking settings will turn on by default while driving. Blocking settings will be pre-set to block all incoming calls and text messages while the vehicle is in motion, but participants will have the ability to override the blocking. Number of unlocks can be monitored through logging in to the Cellcontrol website.

In the bidirectional monitoring arm, the teen will receive an email notification when their parent unlocks their phone while driving and vice versa.

6.4.2 Teen Only Monitoring Group

The blocking settings will turn on by default while driving for both the teen and parent. Blocking settings will be pre-set to block all incoming calls and text messages while the vehicle is in motion, but participants will have the ability to override the blocking. Number of unlocks can be monitored through logging in to the Cellcontrol website.

The teen only monitoring group involves parental monitoring of teen's cellphone use while driving only. The parent will receive an email notification when their teen unlocks their phone while driving. Both parent and teen will drive under the same restrictions, but only the parent will be notified of teen cellphone use.

7 SAFETY MANAGEMENT

7.1 Adverse Event Reporting

Since the study procedures are not greater than minimal risk, SAEs are not expected. If any unanticipated problems related to research involving risks to subjects or others happen during the course of this study (including SAEs) they will be reported to the IRB in accordance with CHOP IRB SOP 408: Unanticipated Problems Involving Risks to Subjects. AEs that are not serious but that are notable and could involve risks to subjects will be summarized in narrative or other format and submitted to the IRB at the time of continuing review.

Enrolled participants will be provided with contact information of a study team member for reporting of any adverse events that occur during data collection. They will be told to contact regarding any occurrence they feel is an adverse event, including but not limited to, moving violations/citations while participating, traffic accidents, DriveID malfunction, etc.

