1.3 Findings from Non-Clinical and Clinical Studies

The largest, most rigorous study of the crash risk associated with distraction from cellphone use was published in the New England Journal of Medicine in January 2014. The authors conducted two studies on the relationship between the performance of secondary tasks, including cell-phone use, and the risk of crashes and near-crashes. To facilitate objective assessment, accelerometers, cameras, global positioning systems, and other sensors were installed in the vehicles of 42 newly licensed drivers (16.3 to 17.0 years of age) and 109 adults with more driving experience.

During the study periods, 167 crashes and near-crashes among novice drivers and 518 crashes and near-crashes among experienced drivers were identified. The risk of a crash or near-crash among novice drivers increased significantly if they were dialing a cell phone (odds ratio, 8.32; 95% confidence interval [CI], 2.83 to 24.42), reaching for a cell phone (odds ratio, 7.05; 95% CI, 2.64 to 18.83), sending or receiving text messages (odds ratio, 3.87; 95% CI, 1.62 to 9.25), reaching for an object other than a cell phone (odds ratio, 8.00; 95% CI, 3.67 to 17.50), looking at a roadside object (odds ratio, 3.90; 95% CI, 1.72 to 8.81), or eating (odds ratio, 2.99; 95% CI, 1.30 to 6.91). Among experienced drivers, dialing a cell phone was associated with a significantly increased risk of a crash or near-crash (odds ratio, 2.49; 95% CI, 1.38 to 4.54); the risk associated with texting or accessing the Internet was not assessed in this population. The prevalence of high-risk attention to secondary tasks increased over time among novice drivers but not among experienced drivers.

The authors concluded that the risk of a crash or near-crash among novice drivers increased with the performance of many secondary tasks, including texting and dialing cell phones. The study was funded by the Eunice Kennedy Shriver National Institute of Child Health and Human Development and the National Highway Traffic Safety Administration.

There is one previous field study using Cellcontrol's cellphone blocking/filtering technology to reduce cellphone use while driving, which was funded by the National Highway and Traffic Safety Administration (NHTSA Contract DOT HS 811 863) and carried out by investigators at the University of Michigan. The abstract of the full report published online in December 2013 states:

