8.4 Regulatory and Ethical Considerations

8.4.1 Data and Safety Monitoring Plan

While there is no data monitoring safety board in place for this study as it is a study with minimal risk and without medical or biological intervention, the research teams at the University of Pennsylvania and the Children's Hospital of Philadelphia, led by the Investigators, will be aware of and will monitor possible areas of risk to the research participants. Weekly team meetings will include discussion of any safety and data issues that are observed. The PIs will be responsible for monitoring the data and safety.

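### Crashes and citations are captured only if participants make contact, no listed survey content asks about them, and no summary by arm or period of these events or of hard decelerations is pre-specified

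*Combined protocol and SAP*

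**What the plan says.** All references are to the combined protocol and SAP.

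- **Event reporting (7.1).** Participants receive contact details for a study team member. "They will be told to contact regarding any occurrence they feel is an adverse event", and the examples given are "moving violations/citations while participating, traffic accidents, DriveID malfunction, etc". Unanticipated problems go to the IRB. Notable non-serious events are summarised for the IRB at continuing review, in a narrative or another format. No tabulation by arm or period is specified.
- **Oversight (8.4.1).** "Weekly team meetings will include discussion of any safety and data issues that are observed". The section does not say that the team asks participants about events.
- **Surveys.** The intake survey (5.2) lists driving habits, opinions and technology use. The end-of-baseline survey (5.4) collects self-reported driving behaviours for the preceding three weeks: "Information includes how often they report texting and driving and self-report cellphone use". The end-of-study survey (5.5) lists feedback, suggestions and "Perceptions of whether their safety had improved with the use of the technology".
- **Device data (5.3).** The app tabulates "Incidence of hard decelerations converted to a" driving score, and it also uploads GPS, accelerometer and timestamp data.
- **Endpoints and analysis (6.1, 6.2, 6.3.2).** Crashes, citations and hard decelerations are in none of the lists. Acceleration is used in secondary objective 7 (2.2) and in the epidemiologic analysis (6.3.2), in both cases as a characteristic of phone unlocks. Phone use at non-zero speeds is summarised across arms.

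**The concern.** The plan names the road events it wants to hear about, then leaves it to participants to volunteer them. Both members of each dyad are enrolled because they admit to texting while driving (3.4.1), so reporting a crash or a ticket is sensitive. Spontaneous reports of such events tend to be incomplete, and the plan has no means of measuring how incomplete. The end-of-study survey would record whether people felt safer, while its listed contents do not ask whether anything happened.

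The pilot's purpose is to show feasibility and to inform the design of a later trial (sections 2 and 6). It would help that trial to know whether crashes and citations can be collected, and to know the rate and spread of hard decelerations. Decelerations can be tabulated later from stored data, although a metric chosen after the data are seen carries less weight. Crashes and citations that nobody asked about may never be recovered.

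**Working it through.** The documents state no crash rate, event count or power for safety, so there is no figure to reproduce. The check has two parts.

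**1. Where each item is collected and where it is analysed**

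| Item | Collected by | In 6.1 or 6.2 | By arm or period in 6.3.2 |
|---|---|---|---|
| Crash | Participant contact (7.1) | No | No |
| Citation | Participant contact (7.1) | No | No |
| Hard decelerations | App, automatically (5.3) | No | No |
| Acceleration at unlock | App, automatically (5.3) | No | No; epidemiologic analysis only |
| Phone use while moving | App, automatically (5.3) | Yes (6.2) | By arm |

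The first three rows are the gap. An analysis at the instant of an unlock cannot give a rate of hard decelerations per hour driven, and so cannot describe an arm or a period.

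**2. What a count of zero would mean**

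Inputs:
- At most 250 people (3.3.2). An equal split, 125 per arm, is assumed.
- Intervention in Weeks 4-8, so 5 weeks (3.1.3). The abstract says participants are followed for 8 weeks after randomisation, so 8 is also shown.
- Crash rate r from 0.05 to 0.20 per person-year. This is an assumption.
- Share of crashes reported, q, of 30%, 60% or 90%. This is also an assumption.

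Formulas: person-years per arm = 125 × weeks/52; expected crashes = person-years × r; probability that an arm reports none = exp(−person-years × r × q), taking counts as Poisson.

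- 5 weeks: 125 × 5/52 = 12.02 person-years; 12.02 × 0.05 = 0.6 and 12.02 × 0.20 = 2.4 crashes per arm.
- 8 weeks: 125 × 8/52 = 19.23 person-years; 0.96 to 3.85 crashes per arm.

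Probability that an arm reports no crash over 5 weeks:

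| Share reported | r = 0.05 | r = 0.10 | r = 0.20 |
|---|---|---|---|
| 30% | 84% | 70% | 49% |
| 60% | 70% | 49% | 24% |
| 90% | 58% | 34% | 12% |
| 100% | 55% | 30% | 9% |

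The last row shows the limit of the fix: even with complete capture, zero crashes in an arm is quite possible. Zero among 125 people gives a one-sided 95% upper limit for the per-person risk of 1 − 0.05^(1/125) = 2.4%.

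Power to detect a doubling of risk with complete capture (two-sided 5% two-proportion test, normal approximation, 125 per arm) is about 6% to 14% over 5 weeks and 8% to 20% over 8 weeks. The approximation is rough with so few events and treats the two members of a dyad as independent. The conclusion that power is very low does not depend on that precision.

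**The case against.** The strongest reply is that this is a feasibility pilot with no crash objective, described as minimal risk ("There are no expected serious adverse events related to the intervention or participation in this study"), and that even perfect capture would yield too few crashes to compare arms. That last part is right, and it is why the fix asks only for description. It does not explain why named events should go unsolicited when two suitable surveys already exist.

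Other parts of the reply also stand:

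- Section 7.1 tells participants explicitly that accidents and citations count, so reporting does not rest wholly on what they feel is adverse.
- Device problems have other routes. Installation errors trigger contact from the study team (4.2), and tampering, deleting the app or disabling Bluetooth triggers an email to the team (1.2). The gap concerns crashes and citations.
- The questionnaires are not in the documents, and the wording of 5.4 is open-ended. One can say only that no listed content covers these events.
- Differential reporting between arms is conjecture. The arms differ in who is notified of unlocks (6.4.1, 6.4.2), not in how crashes reach staff.

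Two stronger readings are tempting and not supported. A reader might infer that the trial cannot describe road safety at all. It can in part: motion data are recorded with no restriction to one arm, and phone use while moving, the risk behaviour itself, is summarised by arm. A reader might also project expected events from the on-road study cited in section 1.3, where "167 crashes and near-crashes among novice drivers and 518 crashes and near-crashes among experienced drivers were identified". The protocol does not give that study's length. Its counts combine crashes with near-crashes found by in-vehicle instruments, and survey items would not recover many of those.

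**Conclusion.** The concern holds as a cheap improvement to data capture and reporting. Crashes and citations depend on participants coming forward, no listed survey content asks about them, and no summary by arm or period of these events or of hard decelerations is planned. Under the assumed rates and reporting shares, an arm would report no crash in the five intervention weeks with probability 12% to 84%, so an absence of reports could not be taken as an absence of crashes. That range rests on maximum enrolment, an equal split and a crash rate that the documents do not supply. The finding about capture needs none of these assumptions. It does not put the feasibility endpoints or the phone-use endpoints in doubt.

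**What to change.** 1. **Surveys (5.4 and 5.5).** Add fixed yes/no items for teens and parents: any crash as driver since the last survey; any police stop or citation since the last survey; and, for each yes, whether the phone was in use. Keep the contact route in 7.1 as an addition.
2. **Endpoints and analysis (6.2 and 6.3.2).** Add one descriptive table giving the number and proportion of participants with at least one crash or citation, and hard decelerations per hour of drive time. Show teens and parents separately, for the baseline period and for the intervention period by arm. Derive the deceleration rate from the vendor's deceleration or accelerometer data, with the definition fixed before analysis.
3. **Interpretation.** State that the table is descriptive, that crashes will be few among at most 250 people, and that no test between arms is planned.

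The cost is a few items in surveys already administered and paid for (8.7.1), and one table from data already uploaded. The items are sensitive, especially for minors, and need IRB review. Solicited counts will look less favourable than spontaneous ones. Because section 5.3 describes decelerations as converted to a score, the hourly rate may have to be derived from the raw data, which takes some programming.
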